**Template 5 Deviations from specifications for age and intervals between study visits (Total Vaccinated Cohort)**

Group		Age	VAC_1-SER_2	
		Protocol	Protocol	Adapted
		from 10 to 15 year	from 30 to 48 days	from 21 to 48 days
dTpaNew Group	N	335	329	329
	n	0	11	8
	%	0.0	3.3	2.4
	range	10 to 15	28 to 74	28 to 74
dTpaPre Group	N	336	329	329
	n	0	10	8
	%	0.0	3.0	2.4
	range	10 to 15	29 to 95	29 to 95

HRV LIQ = HRV vaccine liquid formulation Lot A

HRV LIQ = HRV vaccine liquid formulation Lot B

HRV LIQ = HRV vaccine liquid formulation Lot C

HRV LYO = HRV vaccine HRV Lyophilised formulation

dTpaNew Group = Subjects who received *Boostrix* in new syringe presentation

dTpaPre Group = Subjects who received *Boostrix* in previous syringe presentation

Adapted = interval used for defining the ATP cohorts for immunogenicity

N = total number of subjects with available results

n(%) = number(percentage) of subjects with results outside of the interval

range = minimum-maximum for age and intervals

VAC = vaccination

SER = Blood Sampling

**Template 6 Summary of demography and baseline characteristics (ATP cohort for Immunogenicity)**

		dTpaNew Group N = 335		dTpaPre Group N = 336		Total N = 671	
Characteristics	Parameters or Categories	Value or n	%	Value or n	%	Value or n	%
Age (years) at vaccination dose: 1	Mean						
	SD						
	Median						
	Minimum						
	Maximum						
Gender	Female						
	Male						
Geographic Ancestry	African Heritage / African American						
	American Indian or Alaskan Native						
	White - Arabic / North African Heritage						
	White - Caucasian / European Heritage						
	Other (Hispanic)						
Height (km)	Mean						
	SD						
	Median						
	Minimum						
	Maximum						
Weight (kg)	Mean						
	SD						
	Median						
	Minimum						
	Maximum						
BMI (kg/m  )	Mean						
	SD						
	Median						
	Minimum						
	Maximum						
Gestational week at dose 1	Below 27						
	27 to 32						
	33 to 36						
	Above 36						
	Mean						
	SD						
	Median						
	Minimum						
	Maximum						
Gestational week at delivery	Mean						
	SD						
	Median						
	Minimum						
	Maximum						

		dTpaNew Group N = 335		dTpaPre Group N = 336		Total N = 671	
Characteristics	Parameters or Categories	Value or n	%	Value or n	%	Value or n	%
Number of days between vaccination (dose 1) and delivery	Mean						
	SD						
	Median						
	Minimum						
	Maximum						
Breast feeding	Yes						
	No						
	Never						
Breast feeding (number of times in a day)	Mean						
	SD						
	Median						
	1st Quartile						
	3rd Quartile						
Duration of breast feeding	Mean						
	SD						
	Median						
Formula feeding	Yes						
	No						
Apgar score (1min)	Mean						
	SD						
	Median						
	Minimum						
	Maximum						
	Unknown						
Apgar score (5min)	Mean						
	SD						
	Median						
	Minimum						
	Maximum						
	Unknown						

dTpaNew Group = Subjects who received *Boostrix* in new syringe presentation  
 dTpaPre Group = Subjects who received *Boostrix* in previous syringe presentation  
 N = total number of subjects  
 n(%) = Number(percentage) of subjects in a given category  
 Value = value of the considered parameter  
 SD = standard deviation  
 Height (cm) = Height expressed in centimeters  
 Weight (kg) = Weight expressed in kilograms  
 BMI (kg/m^2) = Body Mass Index expressed in kilograms per meter square

**Template 7 Study population (TVC)**

Study population (Total vaccinated cohort)		
Number of subjects	Combo group	Control group
Planned, N	225	225
Randomised, N (Total Vaccinated Cohort)	224	227
Completed, n (%)	224 (100)	227 (100)
Demographics	Combo group	Control group
N (Total Vaccinated Cohort)	224	227
Females :Males	97:127	115:112
Mean Age, weeks (SD)	8.8 (1.1)	8.8 (1.1)
Median Age, weeks (minimum, maximum)	9 (7, 11)	9 (7, 11)
Most frequent race: Asian - East Asian Heritage, n (%)	224 (100)	226 (99.6)

Combo group = Subjects received DTPa-IPV/Hib vaccine as a single injection at 2, 4 and 6 months of age  
 Control group = Subjects received DTPa-IPV and Hib vaccines at different injection sites at 2, 4 and 6 months of age  
 N = Total number of subjects enrolled in the study  
 n/% = Number/percentage of subjects in a given category  
 SD = Standard Deviation  
 MeaAge = Age calculated from Date of birth to first study vaccination

**Template 8 Summary of household contacts in Spain (Total vaccinated cohort: (subset of subjects in Spain))**

		Household group	
		N =	
Characteristics	Parameters or categories	n or value	%
Household contacts approached	Yes		
	No		
Number of household contacts by vaccinated subject	Mean		
	SD		
	Median		
	1st Quartile		
	3rd Quartile		
Household contact approached	Total		
Eligible Household contact	Total		

N = Total number of subjects vaccinated in Spain  
 n(%) = Number(percentage) of subjects in a given category  
 value = value of the considered parameter

**Template 9 Summary of vaccination of household contacts in Spain (Total cohort for household contacts in Spain)**

	Parameters or Categories	Household Group			
		N =			
				95% CI	
		Value or n	Per	LL	UL
Household contacts who accepted vaccination					
Household contacts who refused vaccination					
Reasons for refusal					
Reason 1					
Reason 2					

dTpa group = Mothers received dTpa during pregnancy  
 Control group = Mothers received placebo during pregnancy  
 N = Total number of eligible household contacts  
 n/Per = number/percentage of subjects reporting  
 95% CI= exact 95% confidence interval; LL = Lower Limit, UL = Upper Limit

**Template 10 Seropositivity and seroprotection rates and GMCs for anti-diphtheria and anti-tetanus antibodies before and one month after the booster vaccination and cord blood sample (ATP cohort for immunogenicity)**

Antibody	Group	Timing	N	≥ assay cut-off*				≥ 0.1 IU/mL				GMC		
				n	%	95% CI		n	%	95% CI		value	95% CI	
						LL	UL			LL	UL		LL	UL
anti-diphtheria	dTpaNew Group	PRE	321	284	88.5	84.5	91.8	83	25.9	21.2	31.0	0.472	0.403	0.553
		POST	321	320	99.7	98.3	100	315	98.1	96.0	99.3	6.784	6.178	7.450
		CORD												
	dTpaPre Group	PRE	319	286	89.7	85.8	92.8	89	27.9	23.0	33.2	0.456	0.392	0.530
		POST	319	319	100	98.9	100	310	97.2	94.7	98.7	6.493	5.915	7.128
		CORD												
anti-tetanus	dTpaNew Group	PRE	321	311	96.9	94.3	98.5	151	47.0	41.5	52.7	0.956	0.835	1.095
		POST	321	321	100	98.9	100	321	100	98.9	100	18.937	17.313	20.713
		CORD												
	dTpaPre Group	PRE	319	314	98.4	96.4	99.5	143	44.8	39.3	50.5	0.899	0.789	1.026
		POST	319	319	100	98.9	100	319	100	98.9	100	18.515	16.851	20.342
		CORD												

dTpaNew Group = Subjects who received *Boostrix* in new syringe presentation  
 dTpaPre Group = Subjects who received *Boostrix* in previous syringe presentation  
 Seroprotection=anti-diphtheria and anti-tetanus antibody concentration ≥0.1 IU/mL  
 \*Assay cut-off is 0.057 IU/mL and 0.043 IU/mL for anti-diphtheria and anti-tetanus respectively  
 GMC = geometric mean antibody concentration calculated on all subjects  
 N = number of subjects with available results  
 n(%)=number(percentage) of subjects with antibody concentrations above the specified cut-off  
 95% CI = 95% confidence interval; LL = Lower Limit, UL = Upper Limit  
 PRE=Pre-booster blood sampling time point  
 POST=Post-booster blood sampling time point

**Template 11 GMC ratio between groups [dTpa Group divided by Control Group] and their 95% CIs for anti-PT, anti-FHA and anti-PRN antigens in cord blood sample (ATP cohort for immunogenicity)**

Antibody	dTpa group		Control group		GMC Ratio (dTpa / Control)		
	N	GMC	N	GMC	GMC ratio	95% CI	
						LL	UL
anti-PT							
anti-FHA							
anti-PRN							

Tdap = Subjects receiving a second dose of Tdap vaccine

N= Number of subjects with available results

95% CI = 95% confidence interval for the adjusted GMC ratio LL = lower limit, UL = upper limit. The associated CI was will be computed using a two-sample t test assuming heterogeneity of variance.

GMC = geometric mean antibody concentration calculated on all subjects

**Template 12 Vaccine responses for anti-PT, anti-FHA and anti-PRN antibody concentration one month after the booster vaccination (ATP cohort for immunogenicity)**

Antibody	Group	Pre-vaccination status	N	Booster response			
				n	%	95% CI	
						LL	UL
anti-PT	dTpaNew Group	S-	142	135	95.1	90.1	98.0
		S+ (<4*assay cut-off)	104	103	99.0	94.8	100
		S+ (≥4*assay cut-off)	71	60	84.5	74.0	92.0
		Total	317	298	94.0	90.8	96.4
	dTpaPre Group	S-	143	131	91.6	85.8	95.6
		S+ (<4*assay cut-off)	114	112	98.2	93.8	99.8
		S+ (≥4*assay cut-off)	61	52	85.2	73.8	93.0
		Total	318	295	92.8	89.3	95.4
anti-FHA	dTpaNew Group	S-	6	6	100	54.1	100
		S+ (<4*assay cut-off)	57	57	100	93.7	100
		S+ (≥4*assay cut-off)	251	242	96.4	93.3	98.3
		Total	314	305	97.1	94.6	98.7
	dTpaPre Group	S-	5	5	100	47.8	100
		S+ (<4*assay cut-off)	55	55	100	93.5	100
		S+ (≥4*assay cut-off)	255	244	95.7	92.4	97.8
		Total	315	304	96.5	93.8	98.2
anti-PRN	dTpaNew Group	S-	52	50	96.2	86.8	99.5
		S+ (<4*assay cut-off)	152	151	99.3	96.4	100
		S+ (≥4*assay cut-off)	117	114	97.4	92.7	99.5
		Total	321	315	98.1	96.0	99.3
	dTpaPre Group	S-	47	47	100	92.5	100
		S+ (<4*assay cut-off)	159	159	100	97.7	100
		S+ (≥4*assay cut-off)	112	111	99.1	95.1	100
		Total	318	317	99.7	98.3	100

dTpaNew Group = Subjects who received *Boostrix* in new syringe presentation

dTpaPre Group = Subjects who received *Boostrix* in previous syringe presentation

S- = Initially seronegative subjects prior to vaccination

S+ = Initially seropositive subjects prior to vaccination

Total = subjects either seropositive or seronegative at pre-vaccination

S- = seronegative subjects (antibody concentration below assay cut off for anti-PT, anti-FHA, anti-PRN)

S+ = seropositive (antibody concentration below assay cut off for anti-PT, anti-FHA, anti-PRN)

Booster response to PT, FHA and PRN antigens is defined as:

- initially seronegative subjects (pre-booster antibody concentration below the assay cut-off) with an increase of at least four times the assay cut-off one month after vaccination,
- initially seropositive subjects with anti-body concentration < four times the assay cut-off with an increase of at least four times the pre-booster antibody concentration one month after vaccination
- initially seropositive subjects with anti-body concentration  $\geq$  four times the assay cut-off with an increase of at least two times the pre-booster antibody concentration one month after vaccination

[figure not shown]
Assay cut-off is 2.693 IU/mL, 2.046 IU/mL and 2.187 IU/mL for anti-PT, FHA and PRN respectively

N = number of subjects with both pre- and post-vaccination results available

n(%) = number(percentage) of subjects with a booster response

95% CI = exact 95% confidence interval, LL = Lower Limit, UL = Upper Limit

**Template 13 Reverse cumulative curve for anti-diphtheria antibody concentration one month after the booster vaccination (ATP cohort for immunogenicity)**

dTpaNew Group = Subjects who received *Boostrix* in new syringe presentation

dTpaPre Group = Subjects who received *Boostrix* in previous syringe presentation

PRE = Pre-vaccination at Day 0

POST = Post-vaccination 1 at Day 28 for primed subject or post-vaccination 2 at Day 56 for unprimed subjects

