5.6.1.3.5. Study Vaccine administration (Amended: 15 July 2015)

- After completing all prerequisite procedures prior to vaccination, one dose of study vaccine will be administered intramuscularly (IM) in the deltoid of the non-dominant arm (refer to Section 6.3 for detailed description of the vaccine administration procedure). If the investigator or delegate determines that the subject's health on the day of administration temporarily precludes vaccine administration, the visit will be rescheduled within the allowed interval for this visit (refer to Table 6).
- The subjects will be observed closely for at least 30 minutes following the administration of the vaccine, with appropriate medical treatment readily available in case of anaphylaxis.
- *The investigators will discuss with the subjects regarding the benefits of cocooning i.e. up to date vaccination of the baby's siblings with DTP-containing vaccines and vaccinating all the household contacts (people living under the same roof) eligible to receive DTP-containing vaccines as per Summary of Product Characteristics (SmPC) of Boostrix and local governmental recommendations in Spain in order to reduce the potential risk of pertussis in neonates. The subjects will be requested to provide the number of household contacts. Additionally the subjects will also be requested for the number of household contacts who refused the visit to site and the reason for refusal for subsequent eligibility determination and vaccination will be documented.*

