##### **6.1.1.1. Analysis of eligible household contacts**

Analysis of eligible household contacts will be performed on the Total cohort for household contacts in Spain.

- Demographic characteristics (age, sex, and race) will be summarised for the eligible household contacts as a whole and per group using descriptive statistics.
- Reasons for refusal of the cocooning vaccination will be summarised for the eligible household contacts as a whole and per group.
- Percentage of household contacts of the infants born to pregnant women vaccinated in Spain who accepted *Boostrix* vaccine as part of an assessment of cocooning among the eligible household contacts will be tabulated as a whole and per group.

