##### **6.1.2. Additional considerations**

Breast feeding status, gestational age at vaccination and the time between vaccination and delivery will be summarised as a whole and per group using descriptive statistics.

The total number of household contacts approached, summary statistics for the number of household contacts by vaccinated subject will be generated in the subset of subjects in Spain.

Note that for a few of the household contacts, since they were later on classified as eligible based on the reasons for refusal, their demographic information is missing.

Apgar score will be summarized at 1 minute and 5 minutes post vaccination. No summary will be provided at 10 minutes as the measurement is optional.

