## **11. ANNEX 1 STANDARD DATA DERIVATION RULE AND STATISTICAL METHODS**

### **11.1. Statistical Method References**

The exact two-sided 95% CIs for a proportion within a group will be the Clopper-Pearson exact CI [Clopper CJ, Pearson ES. The use of confidence or fiducial limits illustrated in the case of binomial. *Biometrika*. 1934;26:404-413].

The 95% CIs of the group GMC ratios will be computed using an ANOVA model on the logarithm10 transformation of the concentrations. The ANOVA model will include the vaccine group as fixed effects. The CI of the group GMC ratios will be computed using a two-sample Welch's t test assuming heterogeneity of variance.

The 95% CI for GMTs/GMCs will be obtained within each group separately. The 95% CI for the mean of log-transformed titre/concentration will be first obtained assuming that log-transformed values were normally distributed with unknown variance. The 95% CI for the GMTs/GMCs will then be obtained by exponential-transformation of the 95% CI for the mean of log-transformed titre/concentration.

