## **12. ANNEX 3: STUDY SPECIFIC MOCK TFL**

The following draft study specific mock TFLs will be used.

The data display, title and footnote are for illustration purpose and will be adapted to the study specificity such as one group and one dose for the study.

These templates were copied from recent studies. Note that there may be few changes between the study specific SAP mock TFL and the final TFLs. These editorial/minor changes will not lead to a SAP amendment.

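### The exact 95% CI planned for the household-contact acceptance rate ignores clustering within a mother's household and is too narrow if two or more correlated eligible contacts per mother are common (minor point)

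*SAP*

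**What the plan says.** Acceptance of *Boostrix* among eligible household contacts in Spain is a secondary objective (Protocol 2.2, SAP 3). SAP 6.1.1.1, repeating Protocol 10.6.1, plans a percentage, "as part of an assessment of cocooning among the eligible household contacts will be tabulated as a whole and per group". Neither section mentions an interval.

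The interval appears in SAP Template 9, which has lower- and upper-limit columns beside the accepted and refused counts. Its footnotes read "N = Total number of eligible household contacts" and "95% CI= exact 95% confidence interval; LL = Lower Limit, UL = Upper Limit". SAP 11.1 fixes the method: "The exact two-sided 95% CIs for a proportion within a group will be the Clopper-Pearson exact CI".

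The cohort is every eligible contact of each infant, with no limit per mother (Protocol 10.4.4, SAP 5.1.4). Protocol 5.6.1.3.5 has the investigator discuss with the mother "vaccinating all the household contacts (people living under the same roof) eligible to receive DTP-containing vaccines". SAP 6.1.2 adds that "summary statistics for the number of household contacts by vaccinated subject will be generated in the subset of subjects in Spain", and Template 8 carries the matching row, "Number of household contacts by vaccinated subject", with mean, SD, median and quartiles. Neither document mentions household clustering, within-household correlation or a cluster-adjusted interval.

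**The concern.** A Clopper-Pearson interval on N contacts uses the variance of N independent yes/no decisions. Decisions within a household need not be independent. The mother receives the cocooning discussion and reports how many contacts there are and how many declined to come to the site. For contacts under 18, consent goes through a parent or representative (Protocol 5.6.2.1). If such contacts tend to accept or refuse together, N overstates the information and the interval comes out too short.

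At stake is the stated precision of one secondary result. No test, success criterion or sample-size claim depends on it.

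**Working it through.** **Does exact mean the single-binomial interval here?** The documents state no precision figure for household contacts, so there is none to reproduce. As a check on the method, Clopper-Pearson limits were computed for the ten rows of Protocol Table 17 (N = 300). Nine rows match, for example 0/300: 0.0-1.2%, 9/300: 1.4-5.6% and 36/300: 8.5-16.2%. The tenth, 35/300, has a printed upper limit of 15.7 against a computed 15.9, which does not bear on this point.

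**Inputs.** From the documents: the unit is the individual eligible contact, the method is Clopper-Pearson, and the cluster is the mother's household. Not in the documents, hence assumed: the number of households (100), the acceptance rate (60%), eligible contacts per household, and the within-household correlation (ICC).

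**Design effect.** DE = 1 + (k - 1) x ICC, with k = (sum of m²)/(sum of m) over household sizes m, and n_eff = N/DE.

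Worked example: 50, 30 and 20 households with 1, 2 and 3 eligible contacts.
- N = 50 + 60 + 60 = 170.
- Sum of m² = 50 + 120 + 180 = 350, so k = 350/170 = 2.059.
- ICC 0.3: DE = 1 + 1.059 x 0.3 = 1.318, n_eff = 129.
- ICC 0.5: DE = 1.529, n_eff = 111.
- ICC 0.8: DE = 1.847, n_eff = 92.

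With 60% accepting (102 of 170), the planned interval is 52.2-67.4%. Clopper-Pearson limits on n_eff are 51.0-68.5%, 50.3-69.2% and 49.3-70.1% respectively.

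**Coverage of the planned interval.** Beta-binomial simulation, 20,000 runs per scenario, 100 households, 60% acceptance, nominal 95%:

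| Eligible contacts per household | ICC 0.3 | ICC 0.5 | ICC 0.8 |
|---|---|---|---|
| 1 in every household | 96% | 96% | 96% |
| 1 in 85%, 2 in 15% | 95% | 95% | 93% |
| 1/2/3 in 50/30/20% | 92% | 90% | 87% |
| 2 in every household | 92% | 90% | 87% |
| 3 in every household | 90% | 86% | 80% |

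At ICC 0.05 coverage is 95-96%.

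**Mean half-width in percentage points, planned versus cluster-adjusted (at ICC 0.3/0.5/0.8).** Two contacts: 7.0 versus 8.0/8.6/9.5. Three contacts: 5.7 versus 7.2/8.1/9.3. One contact: 9.9 versus 10.0. The adjusted interval covers about 96% in the scenarios of the table that have more than one contact in some households.

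**The case against.** The strongest reply is that the premise that matters is missing from the documents. Template 8 counts all contacts, not eligible ones. Protocol 5.6.1.3.5 is compatible with a single eligible contact. Several rules reduce the eligible number:
- Contacts must qualify under the product label and Spanish recommendations (Protocol 4.2), and the vaccine is indicated only from age four (Protocol 1.2.1).
- Pregnant or lactating contacts are excluded (Protocol 4.3).
- Women of childbearing potential must meet contraception and pregnancy-test conditions (Protocol 4.2).
- The mother is a study subject, not a contact.

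This stands. The near-null rows of the table are plausible, and the 80% figure needs three eligible contacts in every household with ICC 0.8.

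Second, the interval is only in a mock table, and SAP 12 says "The data display, title and footnote are for illustration purpose and will be adapted to the study specificity". That lowers the weight of the point but does not remove it. SAP 11.1 is the standing rule for a proportion, and nothing in the SAP would put a clustered method in its place.

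Third, the endpoint is descriptive (SAP 7). That also stands, and it is why the point is minor. An interval labelled 95% still makes a claim about precision.

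Fourth, an effective-sample-size interval can be conservative. With 50 households, two contacts each, 95% acceptance and ICC 0.5, the planned interval already covers 95.0% and the adjusted one 98.6%. This is a real cost.

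**Conclusion.** The plan applies an independent-observations interval to data that may be clustered by household, with no adjustment. The interval is too narrow on two conditions: two or more eligible contacts per mother are common, and their decisions are correlated. Under the assumptions shown, coverage is then roughly 80-92% instead of 95%, and the example interval should be about 1 to 3 points wider on each side. If most households have one eligible contact, coverage is about 93-96% and the effect is small to nil.

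A reader might infer that the reported precision is certainly overstated. The documents do not support that, because they give neither eligible contacts per mother nor any correlation. A reader might also infer from SAP 6.1.2, where a few contacts were later counted as eligible on the strength of their refusal reasons, that the acceptance rate is biased. The documents establish neither a direction nor a size for that, and the present point does not depend on it.

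The percentage stands as planned, and the primary objective is untouched. The remedy is cheap, but the consequence is small.

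**What to change.** Either of two changes to Template 9 is enough.

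1. **Use the mother as cluster.** Keep Clopper-Pearson limits but compute them on n_eff = min(N, p(1 - p)/v), where v = H/(H - 1) x sum over the H mothers of (accepted_i - p x contacts_i)² / N². If all contacts accept or all refuse, v is 0, so set n_eff = H. Apply the same rule overall and per group. The last rule matters: with 30 households, three contacts each, 95% acceptance and ICC 0.8, using n_eff = N when everyone accepts gives 85.1% coverage, against 98.7% with the rule. A plain ratio-estimator t interval is not a good substitute, as it covered less often than the planned interval in 185 of 300 simulated scenarios.

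2. **Delete the lower- and upper-limit columns**, since SAP 6.1.1.1 asks only for the percentage.

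The first needs a few lines of programming and a link from each contact to the mother. It gives a somewhat wider interval, conservative at high acceptance rates. With one contact per mother it reduces to n_eff = H - 1, so almost nothing is lost if there is no clustering. The second costs only the two columns. Neither changes the percentage or who may be vaccinated.
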